22.3. Potentially clinically significant ranges – Adults

1.0

CD14152.SPR118169.SAP.V01

Approved 10-Nov-2022 00:00:00

Test Parameter	Reference range (as per Lab Manual)		Potentially Clinically Significant Ranges (min and/or max limits)	SI Units
	LLN	ULN		
SERUM				
White Blood Cell Count (WBC)	4.00	10.70	<3.0 at post-baseline and ≥3.0 at baseline >15.0 at post-baseline and ≤15 at baseline	x10E9/L
Neutrophils (absolute)	1.60	7.40	<1.5 at post-baseline and ≥1.5 at baseline >9 at post-baseline and ≤9 at baseline	x10E9/L
Eosinophils (absolute)	0.00	0.70	>0.7 at post-baseline and ≤0.7 at baseline	x10E9/L
Basophils (absolute)	0.00	0.20	>0.2 at post-baseline and ≤0.2 at baseline	x10E9/L
Monocytes (absolute)	0.10	0.90	>0.9 at post-baseline and ≤0.9 at baseline	x10E9/L
Lymphocytes (absolute)	1.00	4.00	<0.8 at post-baseline and ≥ 0.8 at baseline >4.0 at post-baseline and ≤ 4.0 at baseline	x10E9/L
Hemoglobin *Male **Female	* 135.00 ** 120.00	* 175.00 ** 160.00	* <100 g/L at post-baseline and ≥ 100 g/L at baseline * ≥200 g/L at post-baseline and < 200 g/L at baseline ** <90 g/L at post-baseline and ≥ 90 g/L at baseline ** ≥180 g/L at post-baseline and < 180 g/L at baseline	g/L
Hematocrit *Male **Female	* 0.40 ** 0.36	* 0.52 ** 0.46	<0.30 at post-baseline and ≥ 0.30 at baseline >0.6 at post-baseline and ≤ 0.6 at baseline	L/L
Platelets	150.00	350.00	<100 at post-baseline and ≥ 100 at baseline >700 at post-baseline and ≤ 700 at baseline	x10E9/L
Sodium	135.00	148.00	<129 at post-baseline and ≥ 129 at baseline >150 at post-baseline and ≤ 150 at baseline	mmol/L
Potassium	3.50	5.30	<3.5 at post-baseline and ≥ 3.5 at baseline >5.5 at post-baseline and ≤ 5.5 at baseline	mmol/L
Calcium - total	2.14	2.62	<2 at post-baseline and ≥ 2 at baseline	mmol/L
Chloride	98.00	110.00	<95 at post-baseline and ≥ 95 at baseline >115 at post-baseline and ≤ 115 at baseline	mmol/L
Glucose	3.90	6.90	<3 at post-baseline and ≥ 3 at baseline >13.9 at post-baseline and ≤ 13.9 at baseline	mmol/L
Creatinine *Male **Female	* 62 ** 44	* 106 ** 80	>1.5 x ULN at post-baseline and ≤1.5 x ULN at baseline	µmol/L
Blood urea nitrogen (BUN)	2.1	8.9	>8.9 at post-baseline and ≤8.9 at baseline	mmol/L
AST	0.00	41.00	>3 x ULN at post-baseline and ≤3 x ULN at baseline	U/L
ALT	0.00	45.00	>3 x ULN at post-baseline and ≤3 x ULN at baseline	U/L
Alkaline phosphatase *Male **Female	* 40 ** 35	* 129 ** 104	>2.5 x ULN at post-baseline and ≤2.5 x ULN at baseline	U/L
Bilirubin total	0.00	21.00	>1.5 x ULN at post-baseline and ≤1.5 x ULN at baseline	µmol/L

This document is confidential.

1.0

CD14152.SPR118169.SAP.V01

CPK				
*Male	20.00	* 200	>2.5 x ULN at post-baseline and ≤2.5 x ULN at baseline	U/L
**Female		** 180	>2.5 x ULN at post-baseline and ≤2.5 x ULN at baseline	
GGT	0.00	65.00	>2.5 x ULN at post-baseline and ≤2.5 x ULN at baseline	U/L
Protein total	60.00	85.00	<50 at post-baseline and ≥50 at baseline >95 at post-baseline and ≤95 at baseline	g/L
Albumin	32.00	55.00	<30 at post-baseline and ≥30 at baseline	g/L
Uric acid	* 0.24	* 0.51	* >0.51 at post-baseline and ≤0.51 at baseline	mmol/L
*Male	** 0.15	** 0.45	** >0.45 at post-baseline and ≤0.45 at baseline	
**Female				
Cholesterol total	0.00	5.17	>7.75 at post-baseline and ≤7.75 at baseline	mmol/L
Triglycerides	0.00	2.25	>3.42 at post-baseline and ≤3.42 at baseline	mmol/L
VITAL SIGNS and WEIGHT				
Pulse rate	N/A	N/A	≤50 bpm and decrease from baseline ≥20 bpm ≥120 bpm and increase from baseline ≥20 bpm	beats/min
Diastolic blood pressure	N/A	N/A	≤45 mmHg and decrease from baseline ≥10 mmHg ≥110 mmHg and increase from baseline ≥10 mmHg	mmHg
Systolic blood pressure	N/A	N/A	≤95 mmHg and decrease from baseline ≥20 mmHg ≥160 mmHg and increase from baseline ≥20 mmHg	mmHg
Weight	N/A	N/A	≥5% increase from baseline ≥5% decrease from baseline	

22.4. Potentially clinically significant ranges – Adolescents

Approved 10-Nov-2022 00:00:00

Test Parameter	Reference range (as per Lab Manual)		Potentially Clinically Significant Ranges (min and/or max limits)	SI Units
	LLN	ULN		
SERUM				
White Blood Cell Count (WBC)	4.00	10.70	<3 at post-baseline and ≥3 at baseline >15.0 at post-baseline and ≤15 at baseline	x10E9/L
Neutrophils (absolute)	1.60	7.40	<1.5 at post-baseline and ≥1.5 at baseline >9 at post-baseline and ≤9 at baseline	x10E9/L
Eosinophils (absolute)	0.00	0.70	>0.7 at post-baseline and ≤0.7 at baseline	x10E9/L
Basophils (absolute)	0.00	0.20	>0.2 at post-baseline and ≤0.2 at baseline	x10E9/L
Monocytes (absolute)	0.10	0.90	>0.9 at post-baseline and ≤0.9 at baseline	x10E9/L
Lymphocytes (absolute)	1.00	4.00	<0.8 at post-baseline and ≥0.8 at baseline >4.0 at post-baseline and ≤4.0 at baseline	x10E9/L
Hemoglobin				
*Male	114.00	* 175.00	<100 g/L at post-baseline and ≥100 g/L at baseline >200 g/L at post-baseline and ≤200 g/L at baseline	g/L
**Female		** 160.00		
Hematocrit				
*Male	0.36	* 0.52	<0.30 at post-baseline and ≥0.30 at baseline >0.6 at post-baseline and ≤0.6 at baseline	L/L
**Female		** 0.46		
Platelets	150.00	420.00	<100 at post-baseline and ≥100 at baseline	x10E9/L

This document is confidential.

1.0

CD14152.SPR118169.SAP.V01

Approved 10-Nov-2022 00:00:00

			>700 at post-baseline and ≤700 at baseline	
Sodium	135.00	148.00	<129 at post-baseline and ≥129 at baseline >150 at post-baseline and ≤150 at baseline	mmol/L
Potassium	3.50	5.30	<3.5 at post-baseline and ≥3.5 at baseline >5.5 at post-baseline and ≤5.5 at baseline	mmol/L
Calcium - total	2.14	2.62	<2 at post-baseline and ≥2 at baseline	mmol/L
Chloride	98.00	110.00	<95 at post-baseline and ≥95 at baseline >115 at post-baseline and ≤115 at baseline	mmol/L
Glucose	3.90	6.90	<3 at post-baseline and ≥3 at baseline >13.9 at post-baseline and ≤13.9 at baseline	mmol/L
Creatinine	31.00	106.00	> 1.5 x ULN 1st IMP dose and ≤ 1.5 x ULN 1st IMP dose	µmol/L
Blood urea nitrogen (BUN)	1.80	7.14	>7.14 at post-baseline and ≤7.14 at baseline	mmol/L
AST	0.00	41.00	>3 x ULN at post-baseline and ≤3 x ULN at baseline	U/L
ALT *Male **Female	5.00	* 30.00 ** 20.00	>3 x ULN at post-baseline and ≤3 x ULN at baseline	U/L U/L
Alkaline phosphatase *Male **Female	0.00	* 389.00 ** 186.00	>2.5 x ULN at post-baseline and ≤2.5 x ULN at baseline	U/L
Bilirubin total	0.00	21.00	>1,5 x ULN at post-baseline and ≤1,5 x ULN at baseline	µmol/L
CPK *Male **Female	2.00	* 251.00 ** 147.00	>2.5 x ULN at post-baseline and ≤2.5 x ULN at baseline >2.5 x ULN at post-baseline and ≤2.5 x ULN at baseline	U/L U/L
GGT *Male **Female	0.00	* 42.00 ** 24.00	>2.5 x ULN at post-baseline and ≤2.5 x ULN at baseline >2.5 x ULN at post-baseline and ≤2.5 x ULN at baseline	U/L U/L
Protein total	60.00	85.00	<50 at post-baseline and ≥50 at baseline >95 at post-baseline and ≤95 at baseline	g/L
Albumin	32.00	55.00	<30 at post-baseline and ≥30 at baseline	g/L
Uric acid *Male **Female	* 0.18 ** 0.13	* 0.51 ** 0.45	>0.51 at post-baseline and ≤0.51 at baseline >0.45 at post-baseline and ≤0.45 at baseline	mmol/L
Cholesterol total	0.00	5.17	>7.75 at post-baseline and ≤7,75 at baseline	mmol/L
Triglycerides	0.00	2.25	>3.42 at post-baseline and ≤3,42 at baseline	mmol/L
VITAL SIGNS and WEIGHT				
Pulse rate	N/A	N/A	≤50 bpm and decrease from baseline ≥20 bpm ≥110 bpm and increase from baseline ≥20 bpm	beats/min
Diastolic blood pressure	N/A	N/A	≤50 mmHg and decrease from baseline ≥10 mmHg ≥90 mmHg and increase from baseline ≥10 mmHg	mmHg
Systolic blood pressure	N/A	N/A	≤90 mmHg and decrease from baseline ≥20 mmHg ≥135 mmHg and increase from baseline ≥20 mmHg	mmHg
Weight	N/A	N/A	≥5% increase from baseline ≥5% decrease from baseline	kg

This document is confidential.

118169_Galderma_SAP_Final_1.0_Version_09 NOV2022

Final Audit Report

2022-11-10

1.0

Created:	2022-11-10
By:	[name] ([contact])
Status:	Signed
Transaction ID:	CBJCHBCAABAA06dOSrvjF-QRaOEyNQIYV9VNcEC5wllM

CD14152.SPR118169.SAP.V01

"118169_Galderma_SAP_Final_1.0_Version_09NOV2022" Histo

ry

Approved 10-Nov-2022 00:00:00

PPD

1.0

CD14152.SPR118169.SAP.V01

Approved 10-Nov-2022 00:00:00

Powered by
Adobe
Acrobat Sign

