### **8.3 Selection of Study Population**

#### **8.3.1 Number of Planned Subjects**

Approximately 750 total subjects are planned to be randomized, including a minimum of 130 adolescent subjects aged 12 to 17 years.

Refer to Section 10.2 for the statistical considerations on which the sample size is based.

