8.2. Key Definitions

Screening Period is a Period of approximately 2-4 weeks before Day 1/Baseline during which subject eligibility is evaluated and standardized background topical therapy is introduced over a run-in Period of at least 2 weeks before Day 1/Baseline.

The Initial Period is defined as Day 1/Baseline to Week 16 (before the Week 16 dose, with last dose at Week 12). If early discontinued during treatment period, it is defined as the period until 4 weeks after last dosing date or early termination date whichever is earlier.

The Maintenance Period is defined as Week 16 (Maintenance Baseline) to Week 48. If early discontinued during treatment period, it is defined as the period until 4 weeks after last dosing date or early termination date whichever is earlier.

Follow-up Period is defined as the post end of treatment period (i.e., 1 day after end of treatment period) to Follow-up visit in respective treatment period.

The Baseline value of the Initial Period will be taken as latest valid value prior to first injection of study drug. For subjects randomized but not treated, the Baseline value will be the latest value prior to the randomization. Week 16 measurements will serve as Baseline measurements for the Maintenance Period (i.e., Maintenance Baseline). If Week 16 measurements are missing for re-randomized subjects, the last valid non-missing measurement in the Initial Period (i.e., before the dosing for Maintenance Period at Week 16 visit) will be taken as the Baseline measurement for the Maintenance Period.

For diary data (e.g., Peak Pruritus (PP) NRS, Sleep disturbance (SD) NRS), the Baseline values will be the weekly prorated average of non-missing subject diary scores reported during the 7 days. A minimum of 4 daily scores out of the 7 days is required to calculate the weekly prorated average score. Refer the details for the analysis visit window for diary data in Section 8.4.

The date of first treatment is defined as the date of first injection of study drug. The date of first treatment is the Baseline date.

The date of last treatment is defined as the date of last injection of study drug.

Study day is defined as the number of days from the date of first treatment and will be calculated as follows:

This document is confidential.

- If the event date \geq date of first treatment, study day = event date – date of first treatment + 1. Study Day 1 is therefore defined as the day of first treatment.

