Shift tables will be generated using the reference ranges (Low, Normal, High and Missing) for hematology and chemistry laboratory data. The number and percentage of subjects shifting from reference ranges between Baseline and each visit (scheduled visits only) will be summarized for the Initial Period and the Maintenance Period. In addition, shift table from Week 16 will be provided for the Maintenance Period. Last, worst and maximum post baseline values will also be included in the shift tables and will include unscheduled visits in the derivation. Worst post baseline value will be defined as the highest or lowest value relative to the reference range.

Summary of the number and percentage of subjects who met criteria of potential clinically significant (CS) value will be summarized (scheduled visits only) for hematology and chemistry laboratory data. Last, worst and maximum post-baseline results will also be included in the summary. Potentially CS ranges for adult and adolescent are listed in sections 22.3 and 22.4.

For statistical and graphical summaries of the laboratory tests, values below or above the limit of detection (e.g. ' < 3 ' or ' >500 ') are substituted with the lower limit of detection minus 1% for values below the lower limit and are substituted with the upper limit of detection plus 1% for values above the upper limit (e.g. ' < 3 ' is substituted by ' 2.97 ', ' > 500 ' is substituted by ' 505 '). In data listings, the values are shown including the $<$ or $>$ sign.

Distribution of Aspartate Aminotransferase (AST), Alanine Aminotransferase (ALT), Alkaline Phosphatase (ALP), Total bilirubin and Creatinine Phosphokinase (CPK) will be displayed graphically as boxplot by treatment group for each scheduled visit and the maximum post-Baseline (including unscheduled visits in the derivation) values for the Initial Period and the Maintenance Period.

By-subject listing will be presented for all laboratory data. By-subject listing for subjects with at least one abnormal result (out of reference range) will be provided for hematology and clinical chemistry. By-subject listing for subjects with at least one potentially CS result will be provided for hematology and clinical chemistry.

This document is confidential.

All laboratory data will be listed for the Safety population.

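### The adolescent creatinine criterion in SAP 22.4 has lost its before/after contrast and contradicts itself, so literal programming would undercount potentially clinically significant creatinine.

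*SAP*

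**What the plan says.** SAP 22.4 lists the limits that make an adolescent laboratory result potentially clinically significant. The creatinine row gives a reference range of 31 to 106 µmol/L and the criterion "> 1.5 x ULN 1st IMP dose and ≤ 1.5 x ULN 1st IMP dose".

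The adult creatinine row in SAP 22.3 reads ">1.5 x ULN at post-baseline and ≤1.5 x ULN at baseline". Total bilirubin in the adolescent table uses the same multiple of the upper limit and reads ">1,5 x ULN at post-baseline and ≤1,5 x ULN at baseline".

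SAP 8.2 fixes the dividing point between the two times: "The Baseline value of the Initial Period will be taken as latest valid value prior to first injection of study drug".

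These limits are operative. SAP 13.2.1 summarises the number and percentage of subjects meeting PCS criteria for hematology and chemistry, and states: "Potentially CS ranges for adult and adolescent are listed in sections 22.3 and 22.4". It adds: "By-subject listing for subjects with at least one potentially CS result will be provided for hematology and clinical chemistry". The SAP's index of tables has PCS chemistry tables for the Initial Period (14.3.4.1.2.6) and the Maintenance Period (14.3.4.1.2.7), and a PCS listing (14.3.4.1.2.9). Protocol 10.1.4.3 also commits to a summary of subjects meeting PCS criteria.

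**The concern.** A PCS rule of this type is meant to pick out subjects who were at or below a limit before treatment and rose above it afterwards. The adolescent creatinine cell names one occasion twice and never says before or after. Taken at face value it asks for a value that is both above and not above the same number.

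The outputs at stake are one laboratory parameter in the PCS tables and the PCS listing, for one age group. A programmer who follows the signed text gets no adolescent creatinine flags whatever the data show. A programmer who sees the problem has to choose the rule without authority from the plan, possibly after seeing data. Because adults and adolescents share the indexed tables, a missing adolescent contribution would not be obvious to a reader of the output.

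**Working it through.** The SAP gives no figure to reproduce here. The check is one of logic, followed by a count of the subjects it touches.

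**Inputs**
- Adolescent creatinine ULN: 106 µmol/L (SAP 22.4).
- Multiple: 1.5 (SAP 22.4).
- Adolescents: "including a minimum of 130 adolescent subjects aged 12 to 17 years" (Protocol 8.3.1), among approximately 750 randomised 2:1.
- Expected maintenance participants: approximately 216, being 190 nemolizumab and 26 placebo (Protocol 8.1).

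**1. The rule as written**

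Threshold = 1.5 x 106 = 159 µmol/L. With the same time label in both halves, the rule is x > 159 and x ≤ 159 for a single value x. That set is empty. A scan from 0 to 1000 µmol/L in steps of 0.1 gave 0 hits in 10,001 values.

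**2. The rule in the form of the other laboratory rows**

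Post-baseline > 159 and baseline ≤ 159 can be met. A baseline of 106 with a post-baseline value of 159.1 or 200 is flagged; a baseline of 200 with a post-baseline value of 400 is not, as intended for a rule about new abnormality.

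**3. Comparison across rows**

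All other laboratory rows in SAP 22.3 and 22.4, whether stated as absolute limits or as multiples of ULN, contrast post-baseline with baseline. The first-dose label occurs in no other row of either table. The vital-sign and weight rows have a different form (change from baseline, with an absolute limit for pulse and blood pressure), so the comparison is with laboratory rows only.

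**4. Subjects affected under literal programming**
- Initial Period: at least 130, which is 130/750 = 17.3% of those randomised. A 2:1 split gives about 130 x 2/3 = 87 on nemolizumab and 130/3 = 43 on placebo. This is approximate because age is not a stratification factor.
- Maintenance Period: the overall proportion expected to continue is 216/750 = 0.288. If adolescents follow it, 130 x 0.288 = 37.4, or roughly 37.

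Under the percentage convention in SAP 17.2.5.2, subjects with an observation are in the denominator. Adolescents would therefore count there while being unable to enter the numerator.

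**The case against.** The strongest reply is that the cell is garbled rather than wrong in intent. Neither half has a preposition, so the obvious reading is that the words after and before were dropped. Given the baseline definition in SAP 8.2, restoring them yields the same rule as the adult row. A competent programmer would query it, and words lost when the PDF was read cannot be wholly excluded. All of this is fair, and it limits the consequence to literal programming. It does not remove the defect: the row is otherwise intact, its wording is unlike any neighbour's, and the visible SAP offers no other definition to fall back on.

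A reader might infer three stronger points that the documents do not support.

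- **That the creatinine rows of the PCS tables would always be zero.** The index lists these tables for the whole Safety Population and for the Enrolled Safety Subjects in Maintenance Period Population, with no age split. Adults, whose rule is sound, would still be counted.
- **That 130 adolescents are affected in both periods.** The 130 is a minimum for randomisation; only Week 16 responders go on to maintenance.
- **That a rise in adolescent creatinine would go unseen.** SAP 13.2.1 summarises chemistry by visit with last, worst and maximum post-baseline values, and adds: "Shift tables will be generated using the reference ranges (Low, Normal, High and Missing) for hematology and chemistry laboratory data". Its listing of subjects with out-of-range results starts at 106 µmol/L and so includes every value above 159. Protocol 9.2.2 has investigators assess each out-of-range result and report clinically significant new or worsened values as adverse events.

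These outputs are a real safeguard, but they do not replace the PCS count. Shift tables class everything above 106 as high, and the abnormal-result listing does not apply the 1.5 x ULN limit.

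**Conclusion.** The point holds as a minor error in an operative cell. As written, the adolescent creatinine criterion cannot be met, and it departs from adult creatinine and from every other laboratory row in the two tables. If programmed literally, at least 130 adolescents in the Initial Period, and roughly 37 in maintenance, could not contribute to the creatinine PCS counts or enter the PCS listing for creatinine.

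The figure of 37 assumes that adolescents continue at the overall planned rate. The number of flags lost cannot be stated, because the documents give no expected rate of creatinine above 159 µmol/L in adolescents; it could be none. Nothing in the primary or key secondary analyses depends on this cell.

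**What to change.** Replace the adolescent creatinine criterion in SAP 22.4 with the post-baseline against baseline wording of the adult creatinine row, keeping the existing 1.5 x ULN limit and the existing adolescent reference range. No new threshold is introduced.

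The cost is one table cell, recorded in a SAP amendment or a dated note to file before the PCS outputs are run. The programming specification for tables 14.3.4.1.2.6 and 14.3.4.1.2.7 and listing 14.3.4.1.2.9 should be checked against the corrected cell. No data collection, sample size or other analysis changes.
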